6.5.1 Rescue Medicine

Appropriate medical equipment and emergency medications, including epinephrine (1:1000), must be available on site in the event of an anaphylactic, vasovagal, or other immediate allergic reaction.

6.6 Dose Modification

Not applicable.

6.7 Intervention After the End of the Study

In the event that one of the vaccines formulations evaluated in this study is demonstrated safe and efficacious and is authorized/approved by the FDA, such vaccine formulation(s) may be offered as soon as possible to participants in this study who received placebo or different formulations, if permitted by local regulations.

7 Discontinuation of Study Intervention and Participant Discontinuation/Withdrawal

7.1 Discontinuation of Study Intervention

[Section 7.1.1](#) and [Section 7.1.2](#) are applicable to Cohort 2 only.

These sections are not applicable to Cohort 1 as they are planned to receive only 1 vaccination in the study.

7.1.1 Temporary Contraindications

Should a participant experience one of the conditions listed below, the Investigator will postpone further vaccination until the condition is resolved. Postponement must still be within the timeframe for vaccination indicated in the SoA.

TCI01: Febrile illness (temperature $\geq 38.0^{\circ}\text{C}$ [$\geq 100.4^{\circ}\text{F}$]) or moderate or severe acute illness / infection on the day of vaccination, according to Investigator judgment

TCI02: Receipt of any vaccine (other than the study vaccine[s]) in the 21 days preceding the second study vaccination or planned receipt of any vaccine in the 30 days following the second study vaccination except for influenza vaccination, which may be received at least 2 weeks before and a minimum of 2 weeks after study vaccines. This exception includes monovalent pandemic influenza vaccines and multivalent influenza vaccines.

7.1.2 Definitive Contraindications

Participants will permanently discontinue (definitive discontinuation) study intervention for the reasons listed below. These participants must not receive any additional dose of study intervention but should continue to be followed for safety. Additional unscheduled visits may be performed for safety reasons and information will be reported in the source documents.

Should a participant experience 1 of the conditions listed below, the Investigator will discontinue vaccination:

- DCI01: Pregnancy, as indicated by a positive urine test
- DCI02: An anaphylactic or other significant allergic reaction to the previous dose of vaccine
- DCI03: SAE assessed as related to the study vaccine following the previous dose of vaccine, based on Investigator's judgment
- DCI04: Grade 3 AE, assessed as related to the study vaccine that, in the opinion of the investigator, may place the participant at unreasonable or significant risk of injury or illness following repeat exposure to study vaccine

In the event of a local or national immunization program with a SARS-CoV-2 or a COVID-19 pandemic vaccine, participants who receive SARS-CoV-2 or a COVID-19 pandemic vaccine at any time during the study will not be withdrawn from the study. As efficacy has not been demonstrated for any of the investigational formulations under evaluation in the current study, it is not required to unblind participants to the VAT00001 study assignment prior to administration of an authorized COVID-19 vaccine.

If the participant receives an authorized approved COVID-19 vaccine, this information would be collected and the participant's data up to the point of receipt of authorized/approved vaccine will be included in the primary analysis for immunogenicity and safety. Participants will continue to be followed for the duration of the study as per scheduled visits and procedures.

7.2 Participant Discontinuation/Withdrawal from the Study

- A participant may withdraw from the study at any time at his/her own request or may be withdrawn at any time at the discretion of the Investigator for safety, behavioral, compliance, or administrative reasons. This is expected to be uncommon.
- The reason for withdrawal should be clearly documented in the source documents and in the CRF: AE, Lost to Follow-up, Protocol Deviation, or Withdrawal by Participant.
- The participant will be permanently discontinued both from the study intervention and from the study at that time.
- If the participant withdraws consent for disclosure of future information, the Sponsor may retain and continue to use any data collected before such a withdrawal of consent.
- If a participant withdraws consent, he/she may request destruction of any samples taken and not tested, and the Investigator must document this in the site study records.
- Withdrawn participants will not be replaced.

Follow-up of Discontinuations

For participants who have prematurely terminated the study, the site should attempt to contact them and complete all scheduled safety follow-ups, except if they specified that they do not want to be contacted again and it is documented in the source document.

For participants where the reason for early termination is lost to follow-up, the site will not attempt to obtain further safety information. See [Section 7.3](#) for definition of “lost to follow-up”.

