§§§§ All participants will be scheduled to attend V07 for blood sampling and 12-Month Safety Follow-up. However, if any participants discontinue the study early, they are still to be followed for safety and are to be contacted with a 12-Month Safety Follow-up call to identify the occurrence of any SAEs and AESIs that had not yet been reported. If discontinuation occurs at a scheduled visit, the participant will be provided a Memory Aid instead of a DC for SAE follow-up (including AESIs) until the 12-Month

Visit (V) / Contact	Collection of information in the CRF	V01	V02	V03	V04	Telephone Call	V05	V06	V07 or Safety Follow-up Call\$\$\$\$
Study timelines (Day [D])		D01	D09	D22	D36	D43	D113	D181	D366
Time Interval (days)			V01 + 8 days	V01 + 21 days	V01 + 35 days	V01 + 42 days	V01 +112 days	V01 + 180 days	V01 + 365 days
Time windows (days)		N/A	[+2 days]	[+7 days]	[+7 days]	[+2 days]	[+7 days]	[+14 days]	[+14 days]
Visit procedures:									

Safety Follow-up call. If a participant discontinues between visits (with no Memory Aid provided yet), the participant will use the last DC received to collect information for the 12-Month Safety Follow-up call.

Table 1.2: Schedule of activities 2 (Cohort 2)

Phase I/II Study, 7 Visits, 2 Telephone Calls, 2 Injections, 6 Blood Sample Time-points, Approximately 13 Months' Duration Per Participant

Visit (V) / Contact	Collection of information in the CRF	V01	Telephone Call 1	V02	V03	V04	Telephone Call 2	V05	V06	V07 or Safety Follow-up Call*****
Study timelines (Day [D])		D01	D09	D22	D30	D36	D43	D134	D202	D387
Time Interval (days)			V01 + 8 days	V01 + 21 days	V02 + 8 days	V02 + 14 days	V02 + 21 days	V02 + 112 days	V02 + 180 days	V02 + 365 days
Time windows (days)		N/A	[+2 days]	[+7 days]	[+2 days]	[+7 days]	[+2 days]	[+7 days]	[+14 days]	[+14 days]
Visit procedures:										
Informed consent	X	X								
Point-of-care SARS-CoV-2 antibody test		X								
Inclusion/exclusion criteria	X	X								
Collection of demographic data	X	X								
Collection of medical history	X Significant Medical History	X								
Physical examination*		X								
Pre-vaccination temperature		X		X						
Urine pregnancy test (if applicable) †		X		X						
Contact IRT system for randomization, participant number, and unique dose number allocation.	X	X								
Contact IRT system for unique dose number allocation.	X			X						

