E18: Health care workers providing direct patient care for COVID-19 patients

E19: Participants with active or prior documented autoimmune disorder (such as potential immune-mediated diseases [pIMDs])

If the participant has a primary physician who is not the Investigator, the site should contact this physician with the participant's consent to inform him / her of the participant's participation in the study. In addition, the site should ask this primary physician to verify exclusion criteria relating to previous therapies, such as receipt of blood products or previous vaccines.

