7.3 Lost to Follow-up

A participant will be considered lost to follow-up if he or she repeatedly fails to return for scheduled visits and is unable to be contacted by the study site.

The following actions must be taken if a participant fails to return to the site for a required study visit or cannot be contacted as planned in the SoA:

- The site must attempt to contact the participant and reschedule the missed visit as soon as possible and counsel the participant on the importance of maintaining the assigned visit schedule and ascertain whether or not the participant wishes to and/or should continue in the study.
- Before a participant is deemed lost to follow-up, the Investigator or designee must make every effort to regain contact with the participant (where possible, 3 telephone calls and, if necessary, a certified letter to the participant’s last known mailing address or local equivalent methods), or at least to determine his/her health status while fully respecting his/her rights. These contact attempts should be documented in the participant’s source documents.
- Should the participant continue to be unreachable, he/she will be considered discontinued from the study with lost to follow-up as reason for discontinuation.

Discontinuation of specific sites or of the study as a whole are handled as part of [Appendix 10.1](#).

8 Study Assessments and Procedures

- Study procedures and their timing are summarized in the SoA. Protocol waivers or exemptions are not allowed.
- Immediate safety concerns should be discussed with the Sponsor immediately upon occurrence or awareness to determine if the participant should continue or discontinue study intervention.
- Adherence to the study design requirements, including those specified in the SoA, is essential and required for study conduct.
- All screening evaluations must be completed and reviewed to confirm that potential participants meet all eligibility criteria. The Investigator will maintain a screening log to record details of all participants screened and to confirm eligibility or record reasons for screening failure, as applicable.

Urine, blood, respiratory samples will be collected as described in the SoA tables ([Section 1.3](#)).

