8.4.1 Time Period and Frequency for Collecting AE and SAE Information

Immediate Post-vaccination Observation Period

Participants will be kept under observation for 30 minutes after each vaccination to ensure their safety. The post-vaccination observation should be documented in the source document.

Reactogenicity

Solicited injection site reactions will be collected from D01 to D08 after each vaccination.

Solicited systemic reactions will be collected from D01 to D08 after each vaccination.

The solicited injection site reactions and systemic reactions that are pre-listed in the diary cards and CRF, together with the intensity scales, are presented in [Appendix 10.3.5.1.1](#).

Unsolicited Adverse Events

Unsolicited AEs include unsolicited non-serious AEs and SAEs. The intensity grading scale for unsolicited non-serious AEs is presented in [Appendix 10.3.5.1.2](#).

Unsolicited non-serious AEs will be collected from D01 to D22 after each vaccination.

SAEs will be collected and assessed throughout the study, from inclusion until 12 months after the last vaccination (up to D366 for Cohort 1 and up to D387 for Cohort 2). However, before the first study intervention administration, only SAEs related to study procedures are to be collected (eg, SAEs related to blood sampling).

Medical occurrences that begin before the start of study intervention but after obtaining informed consent will not be recorded on the AE section of the CRF.

All SAEs will be recorded and reported to the Sponsor or designee immediately and under no circumstance should this exceed 24 hours, as indicated in [Appendix 10.3](#). The Investigator will submit any updated SAE data to the Sponsor within 24 hours of it being available.

Investigators are not obligated to actively seek AE or SAE after conclusion of the study participation. However, if the Investigator learns of any SAE, including a death, at any time after a participant has been discharged from the study, and he/she considers the event to be reasonably related to the study intervention or study participation, the Investigator must promptly notify the Sponsor.

Medically Attended Adverse Events (MAAEs)

MAAEs will be collected at any time during the study.

Adverse Events of Special Interest (AESIs)

AESIs will be collected at any time during the study.

See [Section 8.4.6](#) for the list of AESIs.

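### Protocol Section 7.2 stops safety contact attempts for participants lost to follow-up, while the schedule of activities calls for a month-12 safety call to anyone who discontinues early

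*Protocol*

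**What the plan says.** Section 7.2 of the protocol first gives a general rule for early terminations: "the site should attempt to contact them and complete all scheduled safety follow-ups, except if they specified that they do not want to be contacted". It then makes one exception: "For participants where the reason for early termination is lost to follow-up, the site will not attempt to obtain further safety information", and refers to Section 7.3 for the definition.

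Section 7.3 reserves the label for someone who "repeatedly fails to return for scheduled visits and is unable to be contacted by the study site". Before it is applied, "the Investigator or designee must make every effort to regain contact with the participant": where possible three telephone calls and, if needed, a certified letter, or at least finding out the participant's state of health. If that fails, "he/she will be considered discontinued from the study with lost to follow-up as reason for discontinuation".

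The footnotes to Tables 1.1 and 1.2 in Section 1.3 say that "if any participants discontinue the study early, they are still to be followed for safety and are to be contacted". This contact is by telephone and is meant to pick up SAEs and AESIs not yet reported. The footnotes to SAP Tables 3.1 and 3.2 repeat this. None of the four mentions loss to follow-up.

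**The concern.** Section 7.3 makes a lost participant a discontinued one. The schedule says any participant who discontinues early is called. Section 7.2 says a lost participant is not. Section 8 of the protocol treats adherence to the schedule as required, so sites could reasonably apply different rules.

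The primary safety objective (Table 3.1) covers all participants up to 12 months after the last dose, with SAEs and AESIs throughout the study among its endpoints. Potential immune-mediated diseases are AESIs, and the protocol collects them to study end. Serious illness can itself be a reason why a participant drops out of contact. If so, the people for whom the late call is dropped are not a random subset, and SAE and AESI counts could be too low in some arms.

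**Working it through.** **1. The instructions side by side**

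| Place | Who | Month-12 safety contact |
|---|---|---|
| Protocol 7.2, general rule | Early terminators who have not refused contact | Attempt |
| Protocol 7.2, exception | Lost to follow-up | No attempt |
| Protocol 7.3 | Lost to follow-up | Classed as discontinued |
| Protocol Tables 1.1 and 1.2, footnotes | Any early discontinuation | Call |
| SAP Tables 3.1 and 3.2, footnotes | Any early discontinuation | Call |

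Rows two and five (and four) conflict once row three is applied.

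**2. Who is affected**

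Two conditions must both hold: the Section 7.3 efforts failed when the participant was labelled lost, and the participant could be reached at the planned month-12 date. Active surveillance calls run every two weeks until D181 (Cohort 1) or D202 (Cohort 2). After that the next scheduled contact is D366 or D387. The gap is 366 − 181 = 185 days, and 387 − 202 = 185 days. A participant labelled lost by the end of active surveillance would therefore go at least about six months without a further attempt under Section 7.2, long enough for some to become reachable again.

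**3. What else would capture events**

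Section 8.4.1 applies "if the Investigator learns of any SAE, including a death, at any time after a participant has been discharged from the study", provided the Investigator considers the event reasonably related. It does not require anyone to ask. It does not cover SAEs judged unrelated or non-serious AESIs.

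**4. Size**

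The plan has no loss rate, power or event figure to reproduce. Section 7.2 says only that withdrawal should be uncommon. The denominator is 300 + 140 = 440. The loss rates below are assumptions. With zero events the two-sided 95% Clopper-Pearson upper limit is 1 − 0.025^(1/n).

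| Assumed loss | Without month-12 contact | n with contact | Upper limit, 0 events |
|---|---|---|---|
| 0% | 0 | 440 | 0.83% |
| 1% | 4 | 436 | 0.84% |
| 5% | 22 | 418 | 0.88% |
| 10% | 44 | 396 | 0.93% |

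For one AS03 two-injection arm (n = 90), 10% loss moves the limit from 4.02% to 4.45% (n = 81). For an arm of 30 it moves from 11.57% to 12.77% (n = 27). The effect on precision is small.

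A missed event matters more in a small arm. One SAE in 30 is 3.3% with an exact upper limit of 17.2%; none in 30 is 0% with an upper limit of 11.6%. That arithmetic holds for any missed SAE, whatever the cause, and does not measure the effect of the Section 7.2 sentence.

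**The case against.** The best defence is that Section 7.2 is a deliberate exception. It states the general rule, carves out one group and points to Section 7.3. The schedule footnotes speak of Memory Aids and diary cards, which suggests a participant who can be reached. On that view the only defect is that the footnotes omit the exception. This reading is possible and cannot be excluded. But nothing in the footnotes or their SAP copies points to it, and even a deliberate exception removes an attempt that serves the primary safety objective.

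It is also fair to say that most of the loss comes from the participant being unreachable, since the label follows real effort. That stands, and it limits the point to the single later call.

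Several stronger readings might be inferred; the documents do not support them:

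- That safety information on lost participants is forbidden, or lost by rule. Section 7.2 stops attempts, not receipt, and Section 8.4.1 keeps a reporting duty for related SAEs that become known.
- That missing the D36 visit and the D43 call, then being out of reach for some weeks, is enough to be written off. Section 7.3 requires repeated missed visits as well as failed contact, and the two-weekly calls give many further chances.
- That COVID-19 outcomes as such are primary safety endpoints. Table 3.1 lists them under the secondary efficacy objectives.
- That lost participants are counted as event-free. The SAP promises numbers and percentages on the safety analysis set, generally without replacing missing data. It does not say how unknown 12-month status is handled, and that question would arise for any dropout.
- That the primary physician could be asked for outcomes. Section 5.2 says "the site should contact this physician with the participant's consent", but to inform the physician of participation and to verify exclusion criteria.

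**Conclusion.** The contradiction is real and should be reconciled. It bears on a primary safety objective, but its reach is small: participants still unreachable after the Section 7.3 efforts who might have been reached at D366 or D387. Neither the number lost nor the fraction recoverable can be derived from the documents, and any bias from informative loss cannot be quantified. The 4 to 44 participants rest on assumed loss of 1% to 10% and are an upper bound on those the rule could affect at each rate. Some recovered events would not enter the tables either, because SAP Section 4.4.1 only lists events with onset on or after receipt of an authorized non-study COVID-19 vaccine. This is an inexpensive improvement to follow-up, not a flaw that undermines the safety analysis.

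**What to change.** Remove the lost-to-follow-up exception from Section 7.2, so that it agrees with the footnotes to protocol Tables 1.1 and 1.2 and SAP Tables 3.1 and 3.2. At the planned month-12 date, attempt the scheduled safety call for SAEs and AESIs once for every discontinued participant who has not refused contact, including those lost to follow-up. In the SAP, add the number of participants with unknown 12-month safety status, by arm, alongside the SAE and AESI tables.

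Writing the exception into the footnotes would also make the texts agree, but it would leave the gap in follow-up.

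The cost is one deleted sentence, one added table row and a few telephone attempts, many of which may fail. The schedules already provide the call and a follow-up participation record for those discontinued early.

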7.3 Lost to Follow-up

A participant will be considered lost to follow-up if he or she repeatedly fails to return for scheduled visits and is unable to be contacted by the study site.

The following actions must be taken if a participant fails to return to the site for a required study visit or cannot be contacted as planned in the SoA:

- The site must attempt to contact the participant and reschedule the missed visit as soon as possible and counsel the participant on the importance of maintaining the assigned visit schedule and ascertain whether or not the participant wishes to and/or should continue in the study.
- Before a participant is deemed lost to follow-up, the Investigator or designee must make every effort to regain contact with the participant (where possible, 3 telephone calls and, if necessary, a certified letter to the participant’s last known mailing address or local equivalent methods), or at least to determine his/her health status while fully respecting his/her rights. These contact attempts should be documented in the participant’s source documents.
- Should the participant continue to be unreachable, he/she will be considered discontinued from the study with lost to follow-up as reason for discontinuation.

Discontinuation of specific sites or of the study as a whole are handled as part of [Appendix 10.1](#).

8 Study Assessments and Procedures

- Study procedures and their timing are summarized in the SoA. Protocol waivers or exemptions are not allowed.
- Immediate safety concerns should be discussed with the Sponsor immediately upon occurrence or awareness to determine if the participant should continue or discontinue study intervention.
- Adherence to the study design requirements, including those specified in the SoA, is essential and required for study conduct.
- All screening evaluations must be completed and reviewed to confirm that potential participants meet all eligibility criteria. The Investigator will maintain a screening log to record details of all participants screened and to confirm eligibility or record reasons for screening failure, as applicable.

Urine, blood, respiratory samples will be collected as described in the SoA tables ([Section 1.3](#)).

The maximum amount of blood collected from each participant over the duration of the study, including any extra assessments that may be required, is not planned to exceed 340 mL (cumulative total) (see [Table 8.1](#)). Repeat or unscheduled samples may be taken for safety reasons or for technical issues with the samples.

Table 8.1: Blood sampling per visit

N=440	D1	D09	D22	D30	D36	D113/D134	D181/D202	D366/D387
Vaccination	X		X*					
Safety Labs	Cohorts 1 and 2	Cohort 1 only		Cohort 2 only				
Sera (N=440)	BL0001		BL0002		BL0003	BL0004	BL0005	BL0006
SARS CoV2 Microneut	X		X		X		X	X
Anti-S IgG ELISA	X		X		X		X	X
Anti-N IgG ELISA	X		X		X	X	X	X
Anti-PanCoV IgG ELISA	X							
PBMC/CMI (N=87)	MC0001*		MC0002*		MC0003*			
Whole Blood (N=87)	WB0001*		WB0002*		WB0003*			
COVID PCR on respiratory sample †	Illness visit							
POC Rapid Test ‡	X							

* Cohort 2 only

† 1 swab per illness visit; until day 366/387

‡ Test at site

Guidance and information for the sample collection, preparation, storage, and shipment are provided in the Operating Guidelines.

